## 5.2. Exclusion Criteria

Deviations from exclusion criteria are not allowed because they can potentially jeopardize the scientific integrity of the study, regulatory acceptability or subject safety. Therefore, adherence to the criteria as specified in the protocol is essential.

A subject will not be eligible for inclusion in this study if any of the following criteria apply:

1. Systemic anti-myeloma therapy or an investigational drug ≤14 days or five half-lives, whichever is shorter, preceding the first dose of study drug
2. Plasmapheresis within 7 days prior to the first dose of study drug
3. Prior treatment with a monoclonal antibody within 30 days of receiving the first dose of study drugs
4. Has received prior therapy with an anti-PD-1, anti-PD-L1, or anti PD-L2 agent or with an agent directed to another stimulatory or co-inhibitory T-cell receptor (e.g.,

CTLA-4, OX 40, CD137) and was discontinued from that treatment due to a Grade 3 or higher immune related adverse event (irAE)

5. Current corneal epithelial disease except mild punctate keratopathy
6. Any major surgery within the last four weeks prior to the first dose of study therapy
7. Presence of active renal condition (infection, requirement for dialysis or any other condition that could affect subject's safety). Subjects with isolated proteinuria resulting from MM are eligible, provided they fulfil criteria given in [Table 3](#)
8. Any serious and/or unstable pre-existing medical, psychiatric disorder or other conditions (including lab abnormalities) that could interfere with subject's safety, obtaining informed consent or compliance to the study procedures.
9. Has received prior radiotherapy within 2 weeks of start of study therapy. Subjects must have recovered from all radiation-related toxicities, not require corticosteroids, and not have had radiation pneumonitis. A 1-week washout is permitted for palliative radiation ( $\leq 2$  weeks of radiotherapy) to non-CNS disease.
10. History of (non-infectious) pneumonitis that required steroids, or current pneumonitis
11. Current active liver or biliary disease per investigator assessment defined by the presence of ascites, encephalopathy, coagulopathy, hypoalbuminemia, esophageal or gastric varices, persistent jaundice, or cirrhosis. Note: Stable chronic liver disease (including Gilbert's syndrome or asymptomatic gallstones) or hepatobiliary involvement of malignancy is acceptable if subject otherwise meets entry criteria
12. Malignancies other than disease under study are excluded, except for any other malignancy from which the subject has been disease-free for more than 2 years and, in the opinion of the principal investigators and GSK Medical Monitor, will not affect the evaluation of the effects of this clinical trial treatment on the currently targeted malignancy (RRMM). Subjects with curatively treated non-melanoma skin cancer are allowed.
13. Has known active CNS metastases and/or carcinomatous meningitis. Subjects with previously treated brain metastases may participate provided they are radiologically stable, i.e., without evidence of progression for at least 4 weeks by repeat imaging (note that the repeat imaging should be performed during study screening), clinically stable and without requirement of steroid treatment for at least 14 days prior to first dose of study therapy
14. Evidence of cardiovascular risk including any of the following:
  - a. QTcF interval  $\geq 470$  msec.  
NOTE: The QT interval should be corrected for heart rate by Fridericia's formula (QTcF).
  - b. Evidence of current clinically significant uncontrolled arrhythmias;
    - i. including clinically significant ECG abnormalities including 2nd degree (Type II) or 3rd degree atrioventricular (AV) block.
  - c. History of myocardial infarction, acute coronary syndromes (including unstable angina), coronary angioplasty, or stenting or bypass grafting within six months of Screening.
  - d. Class III or IV heart failure as defined by the New York Heart Association functional classification system ([Appendix 4](#))
  - e. Uncontrolled hypertension
  - f. Presence of cardiac pacemaker (or defibrillator) with a predominantly ventricular paced rhythm, limiting ECG/QTcF analysis.

g. Abnormal cardiac valve morphology ( $\geq$ Grade 2) documented by echocardiogram (subjects with grade 1 abnormalities **CCI** [REDACTED] can be entered on study). Subjects with moderate valvular thickening should not be entered on study.

15. Known immediate or delayed hypersensitivity reaction or idiosyncrasy to drugs chemically related to belantamab mafodotin or pembrolizumab, or any of the components of the study treatment.

16. Pregnant or lactating female.

17. Known active infection requiring antibiotic, antiviral, or antifungal treatment.

18. Known HIV infection.

19. Presence of hepatitis B surface antigen (HBsAg), or hepatitis B core antibody (HBcAb at screening or within 3 months prior to first dose of study treatment

20. Positive hepatitis C antibody test result or positive hepatitis C RNA test result at screening or within 3 months prior to first dose of study treatment.

NOTE: Subjects with positive Hepatitis C antibody due to prior resolved disease can be enrolled, only if a confirmatory negative Hepatitis C RNA test is obtained

NOTE: Hepatitis RNA testing is optional and subjects with negative Hepatitis C antibody test are not required to also undergo Hepatitis C RNA testing

21. Has received a live-virus vaccination within 30 days of planned start of study therapy.  
Note: Seasonal influenza vaccines for injection are generally inactivated flu vaccines and are allowed; however intranasal influenza vaccines (e.g., Flu-Mist) are live attenuated vaccines, and are not allowed.

22. Active autoimmune disease that has required systemic treatment in past 2 years (i.e. with use of disease modifying agents, corticosteroids or immunosuppressive drugs). Replacement therapy (eg, thyroxine, insulin, or physiologic corticosteroid replacement therapy for adrenal or pituitary insufficiency, etc.) is not considered a form of systemic treatment.

23. Has a diagnosis of immunodeficiency or is receiving chronic systemic steroid therapy (in dosing exceeding 10 mg daily of prednisone equivalent) or any other chronic form of immunosuppressive therapy within 7 days prior the first dose of study therapy

24. Has known psychiatric or substance abuse disorder that would interfere with the subject's ability to cooperate with the requirements of the study.

25. Has had an allogenic tissue/solid organ transplant

### 5.3. Screening Failures

Screen failures are defined as subjects who consent to participate in the clinical trial but are never subsequently randomized. In order to ensure transparent reporting of screen failure subjects, meet the Consolidated Standards of Reporting Trials (CONSORT) publishing requirements, and respond to queries from Regulatory authorities, a minimal set of screen failure information is required including Demography, Screen Failure details, Eligibility Criteria.

Individuals who do not meet the criteria for participation in this study (screen failure) may be rescreened. Rescreened subjects must be assigned a new unique subject number that is different from the initial number.

## 5.4. Withdrawal/Stopping Criteria

Subjects will receive study treatment until disease progression, death or unacceptable toxicity (including but not restricted to meeting stopping criteria for significant toxicity as outlined in Section [5.4.1](#)), or completion of pre-assigned treatment by reaching a maximum of 35 treatment cycles. In addition, study treatment may be permanently discontinued for any of the following reasons:

- recurrent Grade 2 pneumonitis
- subject has met any of the protocol defined safety stopping criteria (Section [5.4.1](#))
- deviation(s) from the protocol
- request of the subject or proxy (withdrawal of consent by subject or proxy)
- investigator's discretion
- concurrent illness that prevents further administration of study treatment(s)
- study treatment must be permanently discontinued in case of pregnancy
- subject is lost to follow-up
- study is closed or terminated

The primary reason study treatment was permanently discontinued must be documented in the subject's medical records and electronic case report form (eCRF)

If the subject withdraws the consent and discontinues from treatment due to toxicity, 'adverse event (AE)' will be recorded as the primary reason for permanently discontinuation on the eCRF.

Once a subject has permanently discontinued from study treatment, the subject will not be allowed to be re-entered the study.

After the study treatment discontinuation, subjects will undergo end of treatment assessments 30 days ( $\pm 7$  days) after the last dosing, or prior to the start of new anti-cancer treatment (whichever occurs first). Subjects who discontinued treatment for reasons other than PD will be followed up every 3 weeks until confirmed PD, until initiation of a new anti-cancer therapy or death. All subjects with confirmed PD will be followed for OS and next subsequent anti-cancer therapy every 3 months until the end of study. End of study is defined in Section [5.5.2](#).

The following actions must be taken for subjects who fail to attend the clinic for a required study visit:

- The site must attempt to contact the subject and re-schedule the missed visit as soon as possible.
- The site must counsel the subject on the importance of maintaining the assigned visit schedule and ascertain whether or not the subject wishes to and/or should continue in the study.
- In cases where the subject is deemed 'lost to follow up', the investigator or designee must make every effort to regain contact with the subject (where possible, 3

telephone calls and if necessary a certified letter to the subject's last known mailing address or local equivalent methods). These contact attempts should be documented in the subject's medical record.

- Should the subject continue to be unreachable, only then will he/she be considered to have withdrawn from the study with a primary reason of "Lost to Follow-up".

A subject may withdraw from study treatment at any time at his/her own request, or may be withdrawn at any time at the discretion of the investigator for safety, behavioural or administrative reasons. If a subject withdraws from the study, he/she may request destruction of any samples taken, and the investigator must document this in the site study records.

[figure not shown]
#### 5.4.1. Safety stopping criteria

##### 5.4.1.1. Liver Chemistry Stopping Criteria

**Liver chemistry stopping and increased monitoring criteria** have been designed to assure subject safety and evaluate liver event etiology.

The diagram below illustrates Liver Stopping Event Algorithm ([Figure 3](#)).

**Figure 3 Liver Stopping and Monitoring Event Algorithm**

Refer to [Appendix 5](#) for required Liver Safety Actions and Follow up Assessments.

#### 5.4.1.2. Study Treatment Restart or Rechallenge

If subject meets liver chemistry stopping criteria do not restart/rechallenge subject with study treatment unless:

- GSK Medical Governance approval is granted (as described below),
- Ethics and/or IRB approval is obtained, if required, and
- Separate consent for treatment restart/rechallenge is signed by the subject

If GSK Medical Governance approval to restart/rechallenge subject with study treatment is not granted, then subject must permanently discontinue study treatment and may continue in the study for protocol-specified follow up assessments.

#### 5.4.1.3. QTc Stopping Criteria

If a subject that meets the corrected QT (QTc) interval duration criteria below, study treatment(s) will be withheld.

- QT interval corrected for heart rate by Fridericia's formula (QTcF = QT / CubeRootRR) >530 msec  
OR
- Increase of QTcF by ≥60 msec from baseline

Based on average QTc value of triplicate ECGs to include manual over-read. For example, if an ECG demonstrates a prolonged QT interval, obtain 2 additional ECGs over a brief period (e.g., within approximately 10 minutes of the abnormal ECG, if possible, and approximately 10 minutes apart from each other), and then use the averaged QTc values of the 3 ECGs to determine whether the subjects should have study treatment(s) withheld.

The QTc should be based on single or averaged QTc values of triplicate electrocardiograms obtained over a brief (e.g., 5-10 minute) recording period.

#### 5.4.1.4. Left Ventricular Ejection Fraction (LVEF) stopping criteria

Echocardiography (ECHO) must be performed at Screening and as outlined in the Time and Events Table ([Table 7](#)). Subjects who have an asymptomatic, absolute decrease of >15% in LVEF compared with baseline or an absolute decrease of >10% in LVEF compared with baseline and the ejection fraction is below 50% should temporarily interrupt study treatment and have a repeat evaluation of LVEF within 1 week. ECHO should be repeated every 1 to 2 weeks for 4 weeks or until LVEF recovery to within 15% of baseline or to above 50% and within 10% of baseline depending on which stopping criteria above were met.

- If the LVEF recovers (defined as absolute decrease ≤15% compared to baseline or ≥50% and absolute decrease ≤10% compared with baseline) at any time during the next 4 weeks, after consultation and approval of the GSK Medical Monitor, the subject may be restarted on belantamab mafodotin at a reduced dose. For such

subjects, monitoring of LVEF will be performed 2, 4, and 8 weeks after rechallenge, and then per protocol

- If LVEF does not recover within 4 weeks, treatment with the combination of belantamab mafodotin and pembrolizumab should be permanently discontinued. Ejection fraction should be monitored every 4 weeks for a total of 16 weeks or until resolution

Subjects with Grade 3 or 4 symptomatic left ventricular systolic dysfunction must discontinue treatment with the combination of belantamab mafodotin and pembrolizumab. Ejection fraction should be monitored every 4 weeks for a total of 16 weeks or until resolution. Copies of all ECHOs and cardiology consultations performed on subjects who experience a >15% decrease in LVEF from baseline or >10% decrease in LVEF from baseline and whose cardiac ejection fraction is <50% will require review by a GSK medical monitor. Instructions for submitting qualifying ECHOs/MUGAs are provided in the Study Reference Manual (SRM).

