#### **5.4.1.6. Valvular Toxicity Stopping Criteria**

Subjects who have a new asymptomatic, moderate regurgitation or stenosis by ECHO (Grade 2 mitral/tricuspid/aortic valvular toxicity per National Cancer Institute- Common Toxicity Criteria for Adverse Events [NCI-CTCAE], version 4.03, [NCI, 2010]) should temporarily discontinue study treatment and have a repeat evaluation by ECHO within 1 week. ECHO should be repeated every 1 to 2 weeks for 4 weeks or until valve recovery to baseline.

- If the valve recovers to baseline any time during the next 4 weeks after consultation and approval of the Medical Monitor, the subject may be restarted on belantamab mafodotin at a reduced dose(s). For such subjects, monitoring of the valve via ECHO will then be performed 2 and 4 weeks after rechallenge, and then per protocol.
- If repeat ECHO does not reveal valve recovery to baseline within 4 weeks, then the subject should permanently discontinue study treatment. The valve should continue to be monitored via ECHO every 4 weeks for 16 weeks or until resolution.
- Subjects with a Grade 3 or 4 **CCI** [REDACTED] valvular toxicity must discontinue study treatment. Valvular toxicity should continue to be monitored every 4 weeks for 16 weeks or until resolution. If recovery occurs (return to baseline via imaging AND symptom resolution) within 4 weeks, the subject may receive belantamab mafodotin at a reduced dose after consultation and approval of the Medical Monitor.

Echocardiogram must be performed as outlined in the Time and Event tables ([Table 7](#), [Table 8](#), and [Table 10](#)). Copies of all ECHO(s) and cardiology consultations performed on subjects who experience valvular toxicity will be required by GSK for review. Instructions for submitting qualifying ECHOs are provided in the SRM.

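### Section 5.4.1.4: the LVEF restart bullet omits the link to the criterion that was met, so an ECHO that still meets an interruption criterion counts as recovery

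*Protocol*

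**What the plan says.** Protocol Section 5.4.1.4 has two triggers for a temporary hold. The first is an asymptomatic absolute LVEF fall of more than 15% from baseline. The second is "an absolute decrease of >10% in LVEF compared with baseline and the ejection fraction is below 50% should temporarily interrupt study treatment". ECHO is then repeated over 4 weeks.

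Recovery is worded twice. The sentence on repeat ECHOs sets the target as "within 15% of baseline or to above 50% and within 10% of baseline depending on which stopping criteria above were met". The bullet that permits restart gives its own definition: "defined as absolute decrease ≤15% compared to baseline or ≥50% and absolute decrease ≤10% compared with baseline". If the LVEF recovers in that sense "at any time during the next 4 weeks, after consultation and approval of the GSK Medical Monitor, the subject may be restarted". The dose of belantamab mafodotin is then lowered.

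The next bullet sets the consequence of non-recovery: "If LVEF does not recover within 4 weeks, treatment with the combination of belantamab mafodotin and pembrolizumab should be permanently discontinued". It does not say what counts as recovery.

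**The concern.** The two wordings share the same limits, apart from 50% itself, but only the repeat-ECHO sentence ties each limit to a trigger. The restart bullet joins them with a plain 'or', and it is the place a site will look to decide whether a subject may be dosed again.

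Two decisions depend on the definition: restart within 4 weeks, and permanent discontinuation of both drugs at 4 weeks. Under the bullet as written, a subject who still meets the second interruption criterion could be restarted and would escape the 4-week rule. Under the matched sentence, the same ECHO values allow no restart and lead to discontinuation.

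**Working it through.** **Inputs.** All come from Section 5.4.1.4, except the entry limit of LVEF ≥50% (Section 5.1, Table 3). Write b for baseline LVEF and x for a later LVEF, in whole percentage points.

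- First interruption criterion, C1: b − x > 15.
- Second interruption criterion, C2: b − x > 10 and x < 50.
- Recovery in the restart bullet, as written: (b − x ≤ 15) or (x ≥ 50 and b − x ≤ 10).
- Recovery matched to the trigger: b − x ≤ 15 after C1; x ≥ 50 and b − x ≤ 10 after C2. Requiring both limits when both criteria were met is an inference, because the protocol does not spell out that case.

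**Step 1: the logic of the bullet.** Any fall of 10 or less is also a fall of 15 or less. The second alternative therefore lies wholly inside the first, and the bullet reduces to b − x ≤ 15.

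**Step 2: the overlap with interruption.** A repeat ECHO is recovered under the bullet and still meets C2 when 11 ≤ b − x ≤ 15 and x ≤ 49. That is x from b − 15 up to the smaller of 49 and b − 11.

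| Baseline | Repeat LVEF values in the overlap |
|---|---|
| 50% | 35–39 |
| 55% | 40–44 |
| 58% | 43–47 |
| 60% | 45–49 |
| 62% | 47–49 |
| 64% | 49 only |
| 65% and above | none, since b − 15 ≥ 50 |

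The 11 baselines from 50% to 60% give 5 values each, and baselines 61% to 64% give 4, 3, 2 and 1. The total is 11 × 5 + 10 = 65 baseline/repeat pairs. All 65 count as recovered under the bullet. For a subject held under C2, none does under the matched rule.

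**Step 3: worked cases.**

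| Baseline | At hold | Criterion met | Repeat | Bullet | Matched rule |
|---|---|---|---|---|---|
| 58% | 46% (fall 12) | C2 only | 46% (fall 12) | recovered | not recovered |
| 58% | 40% (fall 18) | C1 and C2 | 46% (fall 12) | recovered | not recovered (by the inference above) |
| 70% | 52% (fall 18) | C1 only | 56% (fall 14) | recovered | recovered |

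In the first case nothing has changed between the hold and the repeat. The third case shows the scope: after C1 alone both definitions reduce to b − x ≤ 15, so they cannot disagree.

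**Step 4: the 50% limit.** The repeat-ECHO sentence asks for more than 50%, the bullet for 50% or more. With the limits matched to the trigger, this matters only at exactly 50%, for example baseline 58%, held at 46%, repeat 50% (fall 8). A subject who enters at exactly 50%, which Table 3 allows, could satisfy the stricter wording only by exceeding baseline.

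**The case against.** The best reply is that the paragraph already answers the question. The sentence just before the bullet gives the same pair of limits in the same order with the matching rule, and the bullet can be read as shorthand for it. The literal reading also makes half of the bullet redundant and calls an unchanged ECHO a recovery, which a careful reader would reject. This stands as evidence of intent. It does not remove the defect: that sentence says how long to repeat ECHOs, while the bullet governs restart and carries the explicit definition. Grouping the bullet as (fall ≤15 or LVEF ≥50%) and fall ≤10 would avoid the overlap, but it is not the natural reading and breaks the paired limits of the preceding sentence.

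The interruption rule also still applies to such an ECHO and has no exemption for a subject already on hold. That is a fair argument against dosing. It leaves the section saying both that the subject has recovered and that treatment should be interrupted, and it does not settle the 4-week rule.

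The safeguards are real. Restart is discretionary, needs Medical Monitor approval and is at a reduced dose. Afterwards "monitoring of LVEF will be performed 2, 4, and 8 weeks after rechallenge". ECHOs in subjects with a ">10% decrease in LVEF from baseline and whose cardiac ejection fraction is <50% will require review by a GSK medical monitor". These limit the harm, but none of them says which definition the Medical Monitor should apply.

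The valve rule in Section 5.4.1.6 is only modest support. It keeps one standard, return to baseline, in its repeat-ECHO sentence ("ECHO should be repeated every 1 to 2 weeks for 4 weeks or until valve recovery to baseline"), its first restart bullet and its 4-week bullet. But its asymptomatic rule has a single trigger, so no matching was needed there.

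**Conclusion.** The concern holds. The restart bullet is wrong as written: for a subject held under the second criterion, it accepts as recovery an ECHO that still meets that criterion. In whole-number LVEF the affected range is baselines 50% to 64% with falls of 11 to 15 points and LVEF below 50%. Subjects held under the first criterion alone are unaffected.

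The result rests on the ordinary reading of 'or' and on percentages taken as absolute LVEF points. The C2-only case follows directly from the text; the case with both criteria met needs the inference stated above. The number of patients affected cannot be estimated from the protocol.

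This is a drafting omission in a safety rule. The interruption thresholds are not in dispute, and ORR, the sample size and the planned analyses are untouched. It should be corrected, because the same ECHO can lead to restart under one wording and permanent discontinuation under the other.

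**What to change.** Use one definition in both the repeat-ECHO sentence and the restart bullet, for example:

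> Recovery is judged against the criterion that led to the hold. (a) Fall of more than 15 points: the fall from baseline is now 15 points or less. (b) Fall of more than 10 points with LVEF below 50%: LVEF is now 50% or more and the fall is 10 points or less. If both criteria were met, both limits apply. This definition also governs permanent discontinuation at 4 weeks.

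Using 50% or more throughout agrees with the entry limit in Table 3 and removes the mismatch at exactly 50%.

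The cost is one short definition in a protocol amendment or clarification letter. It adds no assessments and leaves the thresholds in the restart bullet unchanged.
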